--

[figure not shown]
	
The first visit and first dosing for the open-label extension phase of the study will occur immediately on the day of the last visit of the double-blind period or up to 1 week following the double-blind period. Day 1 of the open-label extension period will be defined as the day of administration of the first dose of difelikefalin in the open-label extension period and will occur preferably on the first dialysis session of the first treatment week (i.e., Monday for subjects on a Monday-Wednesday-Friday dialysis schedule, or Tuesday for subjects on a Tuesday-Thursday-Saturday dialysis schedule).
 
The last dose of open-label difelikefalin will be administered at the last dialysis visit on Week 14, or early termination.
 
Subjects will complete the Skindex-10 scale and 5-D itch scale at Week 4, Week 8, Week 12 and at the end-of-treatment visit, which corresponds to the first dialysis visit following the last dose of difelikefalin given in the open-label extension (i.e., first dialysis on Week 15).
 
Blood samples for clinical laboratory tests will be collected at the end of treatment or early termination visit; in addition, blood samples for analysis of serum potassium will be collected every 2 weeks (on dialysis days), i.e., at Week 2, Week 4, Week 6, Week 8, Week 10 and Week 12 of the open-label extension. Vital signs will be monitored on Day 1, at Week 4, Week 8, Week 12 and at the end of treatment or early termination visit. AEs and concomitant medications will be continuously recorded throughout the open-label treatment period.
 
12-lead ECGs will be monitored at the open-label end of treatment or early termination visit.
 
Follow-up Period
 
A final safety follow-up visit will be conducted in 7 to 10 days:
 
 • After the end-of-treatment visit of the double-blind period for subjects not participating in the open-label extension phase • After the end-of-treatment visit of the open-label extension period for subjects participating in the open-label extension phase • Or after the early termination visit during either the double-blind period or the open-label extension phase

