- Subjects to complete 5-D itch scale (preferably first) and Skindex-10 scale. If the first visit of the week is missed, the subject may complete the worksheets at their next visit for the same week. The questionnaires could be completed before or during dialysis (preferably within 1 hour of the dialysis) but before dosing
- Patient Global Impression of Change
- AE assessment
- Concomitant medications (including antipruritic medications)

Note: The end-of-treatment visit in the double-blind period will be the first dialysis visit following the last dose of investigational product, i.e., first dialysis on Week 13/Day 85, which also corresponds to Day 1 of the open-label extension period.

8.6 Follow-up Period (ONLY for Subjects not Participating in the Open-label Extension Phase)/Day 85 to Day 95

- Pre-dialysis vital signs, including body temperature, heart rate, and blood pressure, will be recorded at the follow-up visit (at 7 to 10 days after end-of-treatment/early termination visit). Heart rate will be measured at each dialysis visit during the follow-up period; if heart rate is clinically significant at visits outside the follow-up visit, the heart rate will be recorded in the eCRF
- WI-NRS worksheets to be completed only on dialysis days
- AEs assessment
- Concomitant medications
- Structured safety evaluation: A list of specific signs/symptoms will be verified with the subject by qualified site study staff once during the follow-up period

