10.2 AE Reporting Period

The AE reporting period begins at the time the ICF is signed by the subject. The AE reporting period ends at the last study visit (end of study/early termination). For SAE reporting period, see Section 10.7.2.

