12.9.1 Adverse Events

All AEs and pre-treatment AEs will be coded using MedDRA to MedDRA SOC and PT for standardisation and summary purposes.

All reported AEs will be included in summary tables by treatment group and by study period, as appropriate. AEs will also be presented in by-subject AE listings.

AEs relative to the double-blind period are identified as any AE:

- With an onset date after the first dose of the investigational product in the double-blind period for subjects who do not enter the open-label extension period.
- With an onset date after the first dose of the investigational product in the double-blind period up to the first dose of difelikefalin in the open-label extension period for subjects who continue into the open-label extension period.

AEs relative to the open-label extension period are identified as any AE with an onset date after the first dose of difelikefalin in the open-label extension period.

A pre-treatment AE is defined as any AE that has an onset before the first investigational product administration.

The number and percentage of subjects experiencing AEs will be summarised by treatment group and by study period. A subject will be counted only once in the incidence count for a MedDRA SOC or PT, although a subject may have multiple occurrences (start and stop) of an event associated with a specific MedDRA SOC or PT.

The incidence and percentage of subjects experiencing treatment-emergent SAEs and AEs leading to investigational product discontinuation will be presented by the appropriate MedDRA SOC and PT.

AEs will also be summarised by severity and by relationship to investigational product for each study period. If the severity and/or relationship to the investigational product of an AE is missing, a worst-case scenario will be assumed (i.e., the AE will be categorised as “severe” and/or “related” to the investigational product). If a subject reports the same AE multiple times the event with the worst severity and the strongest relationship to investigational product will be tabulated.

For each study period, an overall summary table will be provided, presenting for each treatment group, the number and percentage of subjects as well as the number of events for AEs, SAEs, treatment-emergent deaths, treatment-related AEs, treatment-related SAEs, severe AEs, AEs leading to investigational product interruption, AEs leading to investigational product discontinuation and AESIs.

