4.8.1 Adverse Events

AEs data are collected from the time the informed consent form (ICF) is signed by the subject. The AE reporting period ends at the last study contact. Missing dates/partial dates of AEs will be handled as per [Section 4.1.9](#).

AEs relative to the open-label extension period are identified as any AE with an onset date on or after the first dose of difelikefalin in the open-label extension period.

All tabular adverse event summaries will only include AEs relative to the open-label extension period.

An AE will be classified as related to study drug if the relationship to study drug was recorded as 'Certain' or 'Probable/Likely' or 'Possible' in eCRF, as determined by the investigator. An AE will be classified as unrelated to study drug if the relationship to study drug was recorded as 'Unlikely' or 'Unrelated' in eCRF as determined by the investigator.

An SAE is defined as an AE when "Is this AE considered as Serious?" on the "Adverse Event" eCRF page is "Yes".

An AE leading to investigational product interruption is defined as an AE where the action taken with study drug is "Drug Interrupted" on the "Adverse Event" eCRF page. An AE leading to investigational product discontinuation is defined as is defined as an AE where the action taken with study drug is "Drug Withdrawn" on the "Adverse Event" eCRF page. An AE leading to early study termination is defined as an AE where other action taken is "Early Study Termination".

Adverse Events of Special Interest (AESI)

An AESI is a medical occurrence specific to the product or program. Any AE with the following MedDRA PT is to be identified as an AESI:

- gait disturbance
- fall
- dizziness
- somnolence
- seizure
- syncope
- mental status changes
- mood altered
- feeling abnormal
- sinus tachycardia, tachycardia, and tachyarrhythmia
- palpitations

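### AE observation windows differ by study period and by extension entry, so the planned crude AE percentages are not comparable between periods without person-time

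*Protocol*

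**What the plan says.** Protocol 12.9.1 defines the double-blind AE window in two ways. For subjects who do not continue, the criterion is "onset date after the first dose of the investigational product in the double-blind period for subjects who do not enter the open-label extension period"; no closing date follows. Subjects who do continue contribute AEs "up to the first dose of difelikefalin in the open-label extension period for subjects who continue into the open-label extension period".

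For the extension, the protocol rule is "AEs relative to the open-label extension period are identified as any AE with an onset date after the first dose of difelikefalin" in that period, again without a closing date. SAP 4.8.1 takes "any AE with an onset date on or after the first dose of difelikefalin in the open-label extension period", also without one. In practice both windows end when collection ends: at the last study visit (Protocol 10.2) or last study contact (SAP 4.8.1). For non-entrants that is the follow-up visit, "at 7 to 10 days after end-of-treatment/early termination visit" (Protocol 8.6). Protocol 8.7.9 uses the same interval after open-label treatment. The first open-label dose may fall "immediately on the day of the last visit of the double-blind period or up to 1 week following the double-blind period" (Protocol Synopsis, Procedures).

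On the summary measure, Protocol 12.9.1 states: "The number and percentage of subjects experiencing AEs will be summarised by treatment group and by study period". The tables add numbers of events. SAP 4.8.1 does the same by treatment sequence. Duration of treatment is summarised for each period (Protocol 12.6, SAP 4.6), but no AE table uses it as a denominator.

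**The concern.** A crude percentage of subjects with at least one event depends on how long subjects were watched. Here that time depends on the study period. Within the double-blind period it also depends on a post-randomisation fact, namely whether the subject went on to the extension. Entry requires that the subject was not withdrawn, received at least 30 of 36 doses, and had no safety reason against entry in the investigator's opinion (Protocol 5.2, criteria 11, 12 and 15).

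The extension is there partly to collect more safety data over longer exposure (Protocol 2.2), so readers will set the two periods' percentages side by side. Without person-time, a difference could come from the length of the window alone, and a real change in risk could be hidden by it.

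**Working it through.** **Plan's own durations.** 4 + 12 + 1 = 17 weeks without the extension. 4 + 12 + 14 + 1 = 31 weeks with it, or 32 with a one-week gap. Double-blind follow-up ends at Day 85 + 10 = Day 95 (Protocol 8.6). Open-label follow-up ends at Day 99 + 10 = Day 109 (SAP Table 3). All agree with the documents.

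**Windows for completers**, in days from first dose (closing day minus 1):
- Double-blind, entrants: Day 85, or up to 7 days later, gives 84–91.
- Double-blind, non-entrants: Day 85 + 7 to 10 = Day 92–95 gives 91–94.
- Open-label: Day 99 + 7 to 10 = Day 106–109 gives 105–108.

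**Ratios, open-label to double-blind.**
- Against entrants: 105/91 = 1.15 to 108/84 = 1.29.
- Against non-entrants: 105/94 = 1.12 to 108/91 = 1.19.

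Protocol 2.2 and 4.1 count follow-up from the last administration instead. With last doses assumed on Days 82 and 96, the windows become 88–91 days (non-entrants) and 102–105 days (open-label), and the conclusion is the same.

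**Effect of window length alone.** The documents give no AE percentages for this trial, so the incidences p below are assumptions. Under constant hazard, open-label incidence = 1 − (1 − p)^ratio, for entrants:
- p = 10%: 1 − 0.9^1.154 = 11.4% to 1 − 0.9^1.286 = 12.7%.
- p = 30%: 1 − 0.7^1.154 = 33.7% to 1 − 0.7^1.286 = 36.8%.

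**What person-time would show.** With constant hazard, 30% in 84 days and 36.0% in 105 days are the same rate: −ln(0.7)/84 × 36,525 = 155.1 first events per 100 patient-years. If the open-label hazard were 0.8 of the double-blind hazard, the crude percentages would tie, since 1 − 0.7^(0.8 × 105/84) = 30.0%, while the rates would be 155.1 and 124.1.

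**Is the direction forced?** No.
- The open-label percentage is no higher once the open-label hazard falls to 84/108 = 0.78 to 91/105 = 0.87 of the double-blind hazard.
- Take an early-onset Weibull hazard (shape s, assumed) running on through both periods for Difelikefalin/Difelikefalin. The open-label cumulative hazard is then −ln(1 − p) × [((84 + 105)/84)^s − 1]. With s = 0.5 and p = 30% this is 0.357 × 0.5 = 0.178, an incidence of 16.3%. Open-label falls below double-blind for any shape under about 0.84–0.90, depending on the windows used.
- For Placebo/Difelikefalin, suppose the same hazard restarts at the first active dose. Then 30% over 84 days becomes 1 − 0.7^(1.25^0.5) = 32.9%, before any effect of selection.

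**Between arms within the double-blind period.** An entrant's 30% over 84 days becomes 1 − 0.7^(91/84) = 32.0% to 1 − 0.7^(94/84) = 32.9% for a non-entrant. With extension uptake of 90% in one arm and 70% in the other (assumed):
- 0.9 × 30 + 0.1 × 32.9 = 30.3%
- 0.7 × 30 + 0.3 × 32.9 = 30.9%

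The unrounded gap is about 0.6 points. At 50% incidence it is about 0.8 points.

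**The case against.** A reader might infer from the longer window that open-label AE rates must exceed double-blind rates by construction. The documents do not support that. It needs a constant hazard and like populations, whereas Protocol 2.2 says adverse reactions occur early, Protocol 7.1 says dizziness, somnolence, mental status changes and gait disturbances may subside with continued treatment, and the entry criteria select subjects who tolerated the double-blind period. For subjects already on drug these push open-label incidence down.

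A reader might also infer that the windows are unbounded. They are not: collection ends at the last study visit, and the figures above use that limit. Nor are off-drug days peculiar to non-entrants, because an entrant who starts late has up to a week off drug that counts as double-blind.

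It can further be said that safety is descriptive with no inference (Protocol 12.9), that no between-period comparison is planned, that exposure is reported elsewhere, and that counting events through a short follow-up is reasonable for a drug whose half-life in Japanese haemodialysis subjects reached 40.0–49.3 hours after the third dose (Protocol 1.2.2.1). An exposure-adjusted rate assumes a roughly constant hazard, so with early-onset events a longer denominator can dilute it.

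Most of this stands as a limit on the claim. It does not remove it: descriptive percentages still need comparable observation time if periods are read together, and event counts do not supply it. Follow-up events can be kept without being merged into the main window.

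**Conclusion.** This is a cheap improvement, not an error that undermines the trial. AE observation time differs by period and, in the double-blind period, by extension entry. With only crude percentages and event counts, the two periods' AE percentages are not comparable. The window effect taken alone is a factor of 1.15–1.29 against entrants and 1.12–1.19 against non-entrants, or about 4 to 7 percentage points at an assumed 30% incidence under constant hazard. Early onset, events that subside and selection act against it, so the net direction is unknown and may differ between the two treatment sequences. The distortion between randomised arms is under about 1 point in the uptake example, so the documents do not support reading this as a material bias in the double-blind comparison.

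The windows assume completion; early terminators have shorter ones. The double-blind analyses are in a separate SAP (SAP 1) that was not supplied and may already close that window or add rates. The open-label SAP does neither.

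**What to change.** In Protocol 12.9.1 and SAP 4.8.1:
- Close each period's main AE window at a common point relative to dosing, for example the end-of-treatment/early-termination visit, or the first open-label dose if earlier.
- Tabulate separately the AEs that start in follow-up or in the gap before the first open-label dose, so that none are lost.
- Beside the crude percentages, add exposure-adjusted incidence (subjects with a first event per patient-year at risk) for overall AEs, SAEs, AEs of special interest and the most common preferred terms, by treatment or sequence and by period. The cut alone does not equalise the periods: 99 − 1 = 98 days against 84 is still a ratio of 1.17.
- Align the protocol's *after* with the SAP's *on or after* for events on the day of the first open-label dose, so that each falls in one period only.
- Check the double-blind SAP for the same points.

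The cost is SAP wording and an added column from dates already collected. The SAP already makes such a cut elsewhere: open-label concomitant medication ends at the end-of-treatment or early-termination visit (SAP 4.5.1), and the last post-baseline value excludes follow-up (SAP Table 3, note b). The downside is more table content. Because the rate assumes a roughly constant hazard, it should supplement the crude percentages, not replace them.

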12.9.2 Special Situations

All special situations will be coded using MedDRA (when applicable). All reported special situations will be included in a by-subject listing.

12.9.3 Vital Signs

For each study period, summary tables for vital signs will include descriptive statistics for baseline and each post-baseline assessment. Descriptive statistics will be calculated on both the actual values and the change from baseline. Baseline is defined as the last measurement taken on or prior to the first day of dosing for each study period. Note that the Day 1 assessment can be included in the evaluation of baseline if that the assessment is performed prior to dosing.

All vital signs will be listed in by-subject listings, including information such as visit, collection date, and will be sorted by subject identifier and date of assessment.

12.9.4 12-lead ECG

For each study period, baseline and change from baseline in ECG parameters will be summarised at each time point.

All 12-lead ECG data will be listed in a by-subject listing.

12.9.5 Physical Examination

Not applicable as physical examination finding will be recorded through medical history or AEs if clinically relevant.

12.9.6 Clinical Laboratory Tests

For each study period, summaries of actual values and the change from baseline to each time point (when applicable) will be presented for quantitative laboratory parameters.

Laboratory values will be reported in Système International units.

Laboratory test results will be classified according to whether the value was below (L), within (N), or above (H) the laboratory parameter reference range. A summary of treatment-emergent shifts will compare the baseline L/N/H classification for each laboratory test to the L/N/H classification at end of the treatment for each study period. For

serum potassium, shift table comparing the baseline L/N/H classification to each post-baseline L/N/H classification will also be provided.

12.10 Interim Analyses

An interim analysis may be performed. Details will be defined in the SAP.

12.11 Handling of Missing Data

Procedures for managing missing data, imputation for missing or partially missing data will be provided in the SAP.

Definitions of baseline will be specified in the SAP and will include rules for identification of baseline values when assessments are missing at the scheduled baseline visit.

13. STUDY ETHICAL CONSIDERATIONS

13.1 Ethical Conduct of the Study

The study will be conducted according to the principles of the World Medical Association's Declaration of Helsinki [21], and the International Council for Harmonisation (ICH) guidelines for Good Clinical Practice (GCP) [22] as amended. The Sponsor will ensure that the study complies with all local, federal, or country regulatory requirements.

The Investigator must ensure the anonymity of all subjects participating in the study. Each subject will be assigned a unique subject number, and this should be used on all forms associated with the subject's documents or samples that will be supplied to the Sponsor or any party completing testing on behalf of the Sponsor (e.g., blood for central laboratory assessments).

All anonymous data remains the property of the Sponsor.

13.2 Informed Consent

The ICF used for the study must comply with the Declaration of Helsinki, regulatory and legal requirements of China, and ICH guidelines; and must have been approved by the IEC prior to use. The Investigator or an authorised associate must explain orally and in writing the nature of the study and the treatment in such a manner that the subject is aware of potential benefits and risks. Subjects must also be informed that participation is voluntary and that they may withdraw from the study at any time, without prejudice. Subjects must be provided sufficient time to consider participation, including discussion with family members prior to signing the ICF. Documentation of the discussion and the date of informed consent must be recorded in the source documentation. Subjects must give informed consent in writing. If applicable, consent from female partners (who become pregnant during the study) of male subjects will also be acquired.

13.3 Independent Ethics Committee

The protocol, any protocol amendments and consent form for the proposed clinical study and any other documents required by the local IEC must be submitted by the Investigator for review and approval to the IEC. The Investigator must also ensure that the IEC reviews the progress of the study on a regular basis and, if necessary, renews its approval of the study on an annual basis. A copy of the approval letter must be forwarded to the Sponsor before the study is implemented.

Approval by the Human Genetics Resources Administration of China will be obtained prior to study initiating for the different study sites.

13.4 Insurance

The Sponsor confirms that it carries liability insurance which protects non-employee physicians or Investigators against claims for which they may become liable as a result of damages caused by Sponsor products used in clinical studies. Insurance coverage is not

extended to damages that the Investigators or third parties may suffer by reason of acts of commission or omission on the part of such Investigators and that are not in accordance with accepted common medical practices (lege artis procedures). The Sponsor will reimburse the subject for all study-related injuries provided that the injury does not arise from the subject's misuse of the investigational product or failure to follow the Investigator's instructions.

14. QUALITY CONTROL AND QUALITY ASSURANCE

The Investigator must ensure that all trial related site source data, study-related documents and reports will be available, and that the provision of direct access for monitoring and auditing by the Sponsor or its designees will be permitted. In addition, the Investigator must ensure that all trial related site source data, study-related documents and reports will be made available for Sponsor audit and inspection by the appropriate Regulatory Authority and review by the IEC.

Accurate and reliable data collection will be assured by verification and cross-check of the eCRFs against the Investigator's records by the Monitor (source document verification), and the maintenance of a drug dispensing log by the Investigator. The data collected will be entered (double-data entry or EDC) into the study database. A comprehensive validation check program will verify the data and queries will be generated for resolution by the Investigator. Throughout the study, the Sponsor or its designates may review data as deemed necessary.

The following steps will be taken to ensure that the trial is conducted by the investigational site in compliance with the study protocol, GCP, and other applicable regulatory requirements:

- Investigator meeting and/or
- Investigator site initiation
- Routine site monitoring
- Documented protocol and GCP training
- eCRF and query review against source documents
- Collection of local laboratory normal ranges

